6. STUDY ASSESSMENTS AND EVALUATIONS

6.1 Overview

All patients should visit the study center on the days specified within this protocol. The complete Schedule of Assessments for this study is presented in Appendix D.

Safety laboratory assessments including hematology, serum biochemistry, pregnancy test, and urinalysis will be performed locally.

6.2 Baseline Study Assessments

The following information will be collected and procedures will be performed for each patient at screening. Screening should take place within 28 days of start of study treatment and safety laboratory assessments should be done within ≤ 14 days prior to initiation of treatment:

- Written informed consent prior to any other study-related procedures (see Section 13.3)
- Medical history and demographics
- Physical examination (including height and weight)
- ECOG performance status (see Appendix A)
- Vital signs (pulse rate, blood pressure [BP], and body temperature)
- Blood transfusion review
- 12-lead electrocardiogram (ECG)
- Pulmonary function tests (FEV1, FVC, DLCO, TLC, RV)
- Urine pregnancy test for women of child-bearing potential (must be performed within 72 hours prior to the start of treatment). Positive urine pregnancy test should be confirmed with a serum beta human chorionic gonadotropin (β -hCG) test.
- Hematology panel (hematocrit, hemoglobin, mean corpuscular volume, platelet count, red blood cell count, white blood cell [WBC] count, WBC 5-part differential)
- Clinical chemistry panel (sodium, potassium, phosphorus, chloride, creatinine, calcium, venous bicarbonate, albumin, total protein, aspartate aminotransferase [AST], alanine aminotransferase [ALT], alkaline phosphatase [ALP], total bilirubin, lactate dehydrogenase, serum glucose, and blood urea nitrogen)
- Lipid panel (fasting) (high-density lipoprotein [HDL] cholesterol, low-density lipoprotein [LDL] cholesterol, total cholesterol, and triglycerides)
- Urinalysis
- Virology tests (HIV, Hepatitis B surface antigen, Hepatitis B surface antibody, Hepatitis B core antibody, Hepatitis C antibody, HBV-DNA [if required], HCV-RNA [if required])
- Concomitant medication review

CONFIDENTIAL

STUDY DRUG: INCB039110 (ITACITINIB)
FINAL PROTOCOL DATE: 26 OCTOBER 2021

INNOVATIONS STUDY NUMBER: BMT 29
VERSION 4

- AE and infection monitoring. Patients with either pre-transplant positive serology results or unknown viral testing results prior to transplant must have viral load results confirming no evidence of active viral infection within 28 days prior to study treatment.
- cGVHD diagnosis and staging (see Appendix G)
- Chimerism assessment as per institutional standards
- Lee Symptom Scale (see Appendix I)
- Document corticosteroid dosage (total dose/kg and type of corticosteroids)
- Document concomitant cGVHD therapy

6.3 Study Assessment Timing

The treatment period begins on the day the patient receives the first dose of study drug through the point at which the Investigator determines the patient will be permanently discontinued from study drug. Dates for subsequent study visits will be determined based upon this day and should occur as close to the scheduled day as possible taking into consideration the windows of time included in the assessments table. During the Day 1 visit, results from screening visit evaluations should be reviewed to determine whether the patient continues to meet the eligibility requirements as specified in the protocol.

6.3.1 Day 1 of Each Cycle

- Physical examination
- ECOG performance status
- Vital signs (blood pressure, body temperature, and pulse rate after about 5 minutes of rest)
- Blood transfusion review
- Hematology, lipid (fasting), and clinical chemistry panels
- Urinalysis
- Pulmonary function tests at Cycle 4 Day 1 and Cycle 7 Day 1 only (FEV1, FVC, DLCO, TLC, RV)
- Urine pregnancy test for women of child-bearing potential (testing is not required if done within 72 hours prior to the start of treatment on Cycle 1 Day 1). Positive urine pregnancy test should be confirmed with a β -hCG serum test.
- Concomitant medication review
- AE and infection monitoring
- Global cGVHD activity assessments (clinician-reported [Appendix E] and patient-reported [Appendix F])
- cGVHD response assessment (Appendix H) (starting at Cycle 2 through 7, and then every odd-numbered cycle thereafter starting with Cycle 9)

CONFIDENTIAL

STUDY DRUG: INCB039110 (ITACITINIB)
FINAL PROTOCOL DATE: 26 OCTOBER 2021

INNOVATIONS STUDY NUMBER: BMT 29
VERSION 4

- Lee Symptom Scale (Day 1 of Cycles 1 and 7 only; Appendix I)
- Document corticosteroid dosage (total dose/kg and type of corticosteroids)
- Assess relapse of underlying malignancy (at the Investigator's discretion; formal re-staging not required)
- Document concomitant cGVHD therapy
- Dispense study drug, collect unused drug from previous cycle, and check compliance.

6.3.2 Days 8, 15, and 22 of Cycle 1 Only

- Physical examination
- Vital signs (blood pressure, body temperature, and pulse rate after about 5 minutes of rest)
- Hematology, lipid (fasting), and clinical chemistry panels
- Urinalysis
- Concomitant medication review
- AE and infection monitoring
- Document corticosteroid dosage (total dose/kg and type of corticosteroids)
- Document concomitant cGVHD therapy

6.4 Response Assessments

Response criteria (CR, PR, or other [unchanged, mixed response, progression]) based on the 2014 NIH Consensus Development Project on Clinical Trials in cGVHD (see Appendix H for criteria) will be assessed on Day 1 of Cycles 2 through 7; and then every odd-numbered cycle thereafter starting on Day 1 of Cycle 9, as well as the EOT visit.

Patients with GVHD progression, progression of the underlying malignancy, or unacceptable toxicity should be discontinued from the study; patients with stable GVHD or a GVHD response to therapy will continue treatment.

6.5 End-of-Treatment Visit

The follow-up evaluations required after treatment ends (due to the completion of the planned study treatment period, GVHD progression, progression of underlying malignancy, or once the patient is discontinued due to unacceptable toxicity or the decision to discontinue treatment by the patient or the study physician) are specified in Appendix D. This visit should be performed within 7 days and no later than 14 days after discontinuation of study treatment. If treatment is discontinued because of toxicity or any other reason(s) and no study treatment is administered, that visit may fulfill the EOT visit.

The following assessments will be performed at the EOT visit:

- Physical examination

CONFIDENTIAL

STUDY DRUG: INCB039110 (ITACITINIB)
FINAL PROTOCOL DATE: 26 OCTOBER 2021

INNOVATIONS STUDY NUMBER: BMT 29
VERSION 4

- ECOG performance status
- Vital signs (blood pressure, body temperature, and pulse rate after about 5 minutes of rest)
- Urine pregnancy test for women of child-bearing potential
- Blood transfusion review
- Electrocardiogram
- Hematology, lipid (fasting), and clinical chemistry panels
- Urinalysis
- Concomitant medication review
- AE and infection monitoring
- Global cGVHD activity assessment (clinician-reported [Appendix E] and patient-reported [Appendix F])
- cGVHD response assessment (Appendix H)
- Assess relapse of underlying malignancy with Lee Symptom Scale (Appendix I)
- Document corticosteroid dosage (total dose/kg and type of corticosteroids)
- Document concomitant cGVHD therapy

6.6 Follow-up

6.6.1 Safety Follow-Up (30 [\pm 7] Days Following Last Dose of Study Treatment)

A 30-day safety follow-up assessment will be performed after the last dose of itacitinib.

The following assessments will be performed at this visit:

- Physical examination
- ECOG performance status
- Vital signs (blood pressure, body temperature, and pulse rate after about 5 minutes of rest)
- Hematology, lipid (fasting), and clinical chemistry panels
- Urinalysis
- Urine pregnancy test for women of child-bearing potential
- Concomitant medication review
- AE and infection monitoring
- Discuss new GVHD therapies

CONFIDENTIAL

STUDY DRUG: INCB039110 (ITACITINIB)
FINAL PROTOCOL DATE: 26 OCTOBER 2021

INNOVATIONS STUDY NUMBER: BMT 29
VERSION 4

6.6.2 Survival Follow Up (Every 3 Months [\pm 30 Days])

Patients who permanently discontinue the study treatment for reasons other than achieving a GVHD status of CR or PR will be followed for survival, relapse of underlying malignancy, and reporting of new cGVHD therapies approximately every 3 months for 1-year after completion of study drug, and can be contacted by telephone, email, or by a site visit.

6.7 Study Treatment Assessments

6.7.1 Informed Consent

All subjects must take part in the informed consent process. Adequate time must be allowed for the subject to ask questions and make a voluntary decision. No protocol-specific procedures, including screening procedures are to be performed until the subject has signed and dated an IRB-approved informed consent form (ICF). For more details, please see Section 13.3.

6.7.2 Medical History and Demographics

A complete medical history and demographics will be taken at screening. Information to be documented includes, prior medical illnesses and conditions, conditioning regimen, stem cell source, GVHD prophylaxis therapy, disease status at transplant, prior lines of GHVD therapy and surgical procedures.

6.7.3 Physical Examinations (Including Performance Scale and Vital Signs)

A complete physical examination will be done at screening, on Days 1, 8, 15, and 22 of Cycle 1, on Day 1 of each subsequent treatment cycle, at the end-of-treatment (EOT) and 30-day safety follow-up (FU) visits, and at the discretion of the Investigator. They will include documentation of height (screening only), weight, and vital signs collected after the patient has been sitting for at least 5 minutes (blood pressure, body temperature, and pulse rate). Blood transfusions will be reviewed at screening, Day 1 of each cycle and at the EOT visit. The ECOG performance status (see Appendix A) will be done at all visits with a physical exam with the exception of Days 8, 15, and 22 of Cycle 1. Any abnormal or clinically significant findings from the physical examination must be recorded on the appropriate electronic case report form (eCRF) page.

If these assessments are performed within 72 hours of initiation of treatment at the screening visit, an abbreviated physical examination can be done on Day 1 of Cycle 1. Vital signs assessments and ECOG performance status are still required prior to first study drug dose.

6.7.4 Pulmonary Function Test

Pulmonary function test will be performed at screening (within 14 days of Cycle 1 Day 1), Day 1 of Cycle 4 and Cycle 7 and include FEV1, FVC, DLCO (corrected for Hb), TLC and RV.

6.7.5 12-Lead Electrocardiogram

Electrocardiograms will be done at screening, at the EOT visit, and at the discretion of the Investigator. Each will be performed with the patient in a supine position having rested in this position for at least 5 minutes before the reading.

ECG should to be performed immediately prior to any blood sample collections, if possible.

CONFIDENTIAL

STUDY DRUG: INCB039110 (ITACITINIB)
FINAL PROTOCOL DATE: 26 OCTOBER 2021

INNOVATIONS STUDY NUMBER: BMT 29
VERSION 4

6.7.6 Pregnancy Testing

Women of child-bearing potential will have a urine pregnancy test at screening (3 days prior to initiation of treatment), on Day 1 of each cycle, the EOT visit, and during the 30-day follow-up visit. Additional urine pregnancy testing is at the Investigator's discretion. Positive results are to be confirmed with serum beta human chorionic gonadotropin testing.

6.7.7 Laboratory Assessments

Laboratory samples (hematology, lipids [fasting], clinical chemistry, urinalysis, and virology [screening and as clinically indicated]) are to be collected as outlined in Appendix D. Safety laboratory analyses will be performed. Laboratory results will be graded using NCI CTCAE Version 5.

6.7.8 Chimerism Testing

Chimerism will be tested at screening according to institutional standards.

6.7.9 Response and Activity Assessments

Please see Section 9.

6.7.10 Prior and Concomitant Medications

All concomitant medications are to be collected and recorded in the eCRF from the time the patient signs the ICF throughout the patient's participation in the study.

6.7.11 Adverse Event Assessments

Information regarding the occurrence of AEs (including infections) will be collected from the time the patient signs the ICF throughout their participation in the study, including a period of 30 days after the last dose of study drug. Adverse event severity will be determined using the CTCAE Version 5 grading scale. Please see Section 11 for more details.

7. DRUG FORMULATION, AVAILABILITY, ADMINISTRATION, AND TOXICITY INFORMATION

7.1 Itacitinib

Investigational Product	Dosage Form and Strength	Manufacturer
Itacitinib	100 mg	Incyte

Itacitinib 100 mg (free base equivalent) sustained-release tablets contain the active ingredients hypromellose, microcrystalline cellulose, lactose monohydrate, and magnesium stearate.

Itacitinib will be administered orally at a starting dose of 200 mg once QD (2 x 100 mg tablets), and may be taken with or without food.

Itacitinib dose will be increased to 300 mg QD (3 x 100 mg tablets) for patients with NR/SD after 2 months of therapy at 200 mg QD.

CONFIDENTIAL

STUDY DRUG: INCB039110 (ITACITINIB)
FINAL PROTOCOL DATE: 26 OCTOBER 2021

INNOVATIONS STUDY NUMBER: BMT 29
VERSION 4

Patients may have dose reductions or interruptions of itacitinib during the course of treatment based on AEs, clinical evaluation, and laboratory assessments. See Section 8.1 for dose modifications of study drug.

Patients are permitted to remain on itacitinib treatment until withdrawal from study treatment is considered necessary as per Section 3.3.

7.1.1 Labeling, Packaging, and Supply

Incyte Corporation will provide itacitinib tablets to the sites in high-density polyethylene bottles. All Incyte Corporation investigational product labels will be in the local language and will comply with legal requirements.

At each visit, patients will be dispensed sufficient supplies until the next visit. Study drug compliance will be assessed at each patient visit. The research staff will count and document the amount of study drug taken and returned by the patient. The batch number of the study drug dispensed to the patient should be entered on the CRF, if applicable.

The immediate packaging will contain a statement to conform with U.S. Food and Drug Administration (FDA) Investigational New Drug (IND) requirements as follows: Caution: New Drug - Limited by Federal (or United States) law to investigational use.

All study drugs must be kept in a secure place under appropriate storage conditions.

Itacitinib should be stored at ambient conditions (15°C to 30°C, or 59°F to 86°F) per the IB.

Sarah Cannon Development Innovations (Innovations) representatives must be granted access on reasonable request to check drug storage, dispensing procedures, and accountability records.

7.1.2 Preparation and Administration of Itacitinib

Itacitinib is administered orally. No preparation is required.

7.1.3 Instructions for Patients for Handling Itacitinib

Patients must be instructed in the handling of itacitinib as follows:

- To store the bottles at room temperature, in a safe place and out of the reach of children
- To only remove the number of tablets needed at the time of administration
- Not to remove tablets in advance of the next scheduled administration
- To make every effort to take doses on schedule
- To report any missed doses
- To take tablets with a glass of water
- Not to take another dose if vomiting occurs after taking the study medication, but rather wait for the next scheduled dose.
- On days of clinic visits, tablets can be taken before the visit or at the clinic after blood samples are collected.
- To bring all used and unused bottles of study medication to the site at each visit.

CONFIDENTIAL

STUDY DRUG: INCB039110 (ITACITINIB)
FINAL PROTOCOL DATE: 26 OCTOBER 2021

INNOVATIONS STUDY NUMBER: BMT 29
VERSION 4

If the patient misses a dose of study drug, the patient should take the dose as soon as possible. If the next dose is due in less than 12 hours, however, the patient should skip the missed dose and take the next dose as scheduled.

If vomiting is persistent, the patient should contact the Investigator.

Study drug will be dispensed and compliance will be assessed by pill counts on Day 1 of each cycle. The research staff will count and document the amount of study drug taken and returned by the patient.

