1.2 Potential Risks and Benefits of the Treatment Regimen

Adverse events (AEs) that have been most frequently reported in at least 10% of all subjects receiving itacitinib monotherapy include constipation, anemia, thrombocytopenia, diarrhea, nausea, fatigue, and upper respiratory tract infection.

As a result of itacitinib-mediated immunomodulation, an increased incidence of infections could possibly occur with itacitinib therapy. Strict clinical monitoring is indicated to identify and treat infections in study subjects should they occur.

Because of the potential for myelosuppression, patients will have hematologic parameters closely monitored during clinical studies. If there are clinically relevant declines in hematology parameters, therapy may be interrupted until resolution or discontinuation. Since itacitinib also has the potential to cause white blood cell (WBC) margination (i.e., a transient decrease in

CONFIDENTIAL

STUDY DRUG: INCB039110 (ITACITINIB)
FINAL PROTOCOL DATE: 26 OCTOBER 2021

INNOVATIONS STUDY NUMBER: BMT 29
VERSION 4

absolute neutrophil count [ANC]), assessment of hematology parameters should be performed before study drug administration and at all applicable study visits.

As described previously, murine models of JAK/STAT inhibition using both ruxolitinib and itacitinib have demonstrated a decrease in the expression of CXCR3, reduction of GVHD, preservation of the beneficial graft-versus-tumor effect, and improvement in survival. To the extent that the thrombocytopenia and anemia observed with ruxolitinib are due to the inhibition of JAK2-mediated erythropoiesis and thrombopoiesis, a selective JAK1 inhibitor would likely be associated with a lower incidence of thrombocytopenia and anemia, while still resulting in a significant reduction in the production and the signaling of inflammatory and immune cytokines. It is therefore of interest to evaluate a selective JAK1 inhibitor in this setting given the hematologic complications associated with GVHD.

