ANC is $<0.5 \times 10^9/L$, suspected as unrelated to study treatment (e.g., GVHD, active cytomegalovirus viremia)	
 • Reduce dose by 1 dose level. • Monitor ANC count as clinically indicated. • Resume previous dose if ANC count is $\geq 0.5 \times 10^9/L$ for more than 7 days.
ANC is $<0.5 \times 10^9/L$, suspected as related to study treatment	
 • Interrupt for up to 14 days. • Monitor ANC count as clinically indicated. • Resume at a reduced dose if ANC count is $\geq 0.5 \times 10^9/L$ for more than 7 days. If the patient's ANC count remains at $\geq 0.5 \times 10^9/L$ for more than 7 days after resuming treatment at a lower dose, the previous dose may be resumed.
Platelet count is $<10 \times 10^9/L$, or platelet count has decreased by $\geq 50\%$ from baseline, suspected as unrelated to study treatment	
 • Reduce dose by 1 dose level. • Monitor platelet count as clinically indicated. • Resume at previous dose if platelet count returns to $\geq 20 \times 10^9/L$ for more than 7 days.
Platelet count is $<10 \times 10^9/L$, or platelet count has decreased by $\geq 50\%$ from baseline, suspected as related to study treatment	
 • Interrupt for up to 14 days. • Monitor platelet count as clinically indicated. • Resume at a reduced dose if platelet count returns to $\geq 20 \times 10^9/L$ for more than 7 days. If the patient's platelet count remains at $\geq 20 \times 10^9/L$ for an additional 7 days, the previous dose of may be resumed.
Other Toxicities	
Any Grade 1 or Grade 2 toxicity	
 • Continue treatment and manage the toxicity. • Monitor as clinically indicated.
Any Grade 3 toxicity, if clinically significant and not manageable by supportive care	
 • Interrupt up to 14 days until toxicity resolves to \leq Grade 1. • Restart at same dose; if assessed as related to itacitinib, restart at next lower dose and monitor as clinically indicated.
Any recurrent Grade 3 toxicity at 100 mg	
 • Discontinue study treatment; follow-up per protocol.

CONFIDENTIAL

STUDY DRUG: INCB039110 (ITACITINIB)
FINAL PROTOCOL DATE: 26 OCTOBER 2021INNOVATIONS STUDY NUMBER: BMT 29
VERSION 4

Table 2 Guidelines for Interrupting and Restarting of Itacitinib

Adverse Event	Action Taken
QD dose	Exceptions require Study Chair approval.

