- c Safety laboratory assessments including hematology, lipids (fasting), clinical chemistry, pregnancy test, and urinalysis will be performed locally. Additional assessments to be performed during the screening period:
 - Blood transfusion review
 - Virology tests (HIV, Hepatitis B surface antigen, Hepatitis B surface antibody, Hepatitis B core antibody, Hepatitis C antibody, HBV-DNA [if required], HCV-RNA [if required])

CONFIDENTIAL

INNOVATIONS STUDY NUMBER: BMT 29

VERSION 4

- Concomitant medication review
- cGVHD diagnosis and staging
- Chimerism assessment as per institutional standards
- Lee Symptom Scale
- Document corticosteroid dosage (total dose/kg and type of corticosteroids)
- Document concomitant cGVHD therapy

The following screening parameters should be done \leq 14 days prior to initiation of treatment:

- Pulmonary function tests (FEV1, FVC, DLCO (corrected for Hb), TLC and RV)
- medical history and demographics (includes conditioning regimen, stem cell source, GVHD prophylaxis therapy, disease status at transplant and prior lines of GHVD therapy), physical examination (including height and weight), Eastern Cooperative Oncology Group (ECOG) performance status, vital signs, electrocardiogram (ECG)
- **hematology:** hematocrit, hemoglobin, mean corpuscular volume, platelet count, red blood cell count, white blood cell (WBC) count, WBC 5-part differential
- **clinical chemistry (lipids in a fasting state):** sodium, potassium, phosphorus, chloride, creatinine, calcium, venous bicarbonate, albumin, total protein, aspartate aminotransferase (AST), alanine aminotransferase (ALT), alkaline phosphatase (ALP), total bilirubin, lactate dehydrogenase, serum glucose, and blood urea nitrogen, lipids high-density lipoprotein (HD) cholesterol, low-density lipoprotein (LDL) cholesterol, total cholesterol, and triglycerides
- **urinalysis**
- screening pregnancy test (urine)

If these assessments are performed within 72 hours of initiation of treatment, they do not need to be repeated on Cycle 1 Day 1 with the exception of the ECOG performance status, an abbreviated physical examination, and vital signs, which are required prior to first study dose. Vital signs (blood pressure, body temperature, and pulse rate) are checked at every visit prior to blood work and study treatment and at the discretion of the Investigator (see Section 6.7.3).

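### Section 7.1.3 allows dosing before the visit although Section 1.2 asks for hematology before dosing; visit ANC values may mix pre-dose and post-dose samples with no required record of which is which

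*Combined protocol and SAP*

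**What the plan says.** Section 1.2 (potential risks and benefits) states that "itacitinib also has the potential to cause white blood cell (WBC) margination (i.e., a transient decrease in" the absolute neutrophil count, and concludes that "assessment of hematology parameters should be performed before study drug administration and at all applicable study visits".

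Section 7.1.3 (patient handling instructions) gives two options for visit days: "On days of clinic visits, tablets can be taken before the visit or at the clinic after blood samples are collected". The amendment summary shows that this sentence replaced an instruction not to take study drug on visit days until blood had been drawn.

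Appendix D, footnote c, adds an order of procedures: "Vital signs (blood pressure, body temperature, and pulse rate) are checked at every visit prior to blood work and study treatment". It does not say whether blood is drawn before or after the dose.

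Hematology is scheduled on Day 1 of every cycle and on Days 8, 15 and 22 of Cycle 1 (Sections 6.3.1 and 6.3.2). Table 2 in Section 8.1 acts on an ANC below 0.5 x 10^9/L: interruption for up to 14 days if drug-related, reduction by one dose level if not. Neither row says when the sample is taken relative to the dose.

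**The concern.** The only reason Section 1.2 gives for the timing of hematology is a fall in ANC that is transient and caused by the drug. Sampling before the dose is the safeguard against reading that fall as neutropenia. A patient who takes the tablets at home before the visit removes the safeguard while following the protocol exactly.

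Two things are at stake. First, a patient whose ANC is close to 0.5 x 10^9/L could meet a Table 2 threshold because of sample timing rather than marrow function. Under Sections 11.1.5.1 and 11.3.3, a laboratory result that requires a study drug adjustment is reported as an adverse event, so the same sample could add an event to the safety tables. Second, the laboratory summaries would pool pre-dose and post-dose ANC values without labels. Safety and tolerability is a stated secondary objective (Section 2.2).

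**Working it through.** **Step 1: can one visit satisfy all three passages?**

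| Visit-day option in 7.1.3 | Section 1.2, hematology before dosing | Appendix D footnote c, vital signs before study treatment |
|---|---|---|
| Tablets at the clinic after the draw | met | can be met |
| Tablets before the visit | not met | not met |

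The second option is explicitly allowed, so the passages cannot all be followed.

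**Step 2: how many samples are open to it?** From Day 8 through Cycle 7 Day 1, the primary assessment, the scheduled on-treatment draws are Days 8, 15 and 22 of Cycle 1 (3) and Day 1 of Cycles 2 to 7 (6), so 3 + 6 = 9 per patient. Cycle 1 Day 1 and screening precede the first dose and are not affected.

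**Step 3: can the samples be separated later?** Compliance is checked by pill counts on Day 1 of each cycle (Section 7.1.3), which give no clock times. The current text requires neither the time of the last dose nor the time of the draw. The eCRF is not among the documents, so whether it holds these fields is unknown.

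**Step 4: which ANC values could be misread?** The plan gives no figure for the fall, so there is nothing to reproduce. Let d be an assumed fractional post-dose fall. A post-dose sample reads (pre-dose ANC) x (1 − d), which is below 0.5 when the pre-dose ANC is below 0.5/(1 − d). The values at risk run from 0.50 up to that limit. The entry criterion, ANC >1,000/mm³, equals 1.0 x 10^9/L, so the limit lies 1 − 0.5/(1 − d) below the entry floor.

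| Assumed d | 0.5/(1 − d), x 10^9/L | Distance below entry floor |
|---|---|---|
| 10% | 0.5/0.90 = 0.56 | 44% |
| 20% | 0.5/0.80 = 0.625 | 37.5% |
| 30% | 0.5/0.70 = 0.71 | 29% |
| 40% | 0.5/0.60 = 0.83 | 17% |
| 50% | 0.5/0.50 = 1.00 | 0% |

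At an assumed 20%, a patient's pre-dose ANC must already have dropped to below 0.625, at least 37.5% under the entry floor, before sample timing alone can produce a reading under 0.5. Only a fall of 50% would bring the band up to the entry floor.

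**The case against.** The strongest reply is that there is no contradiction. The sentence in Section 1.2 can be read as naming two occasions, before starting the drug and at later visits, and the schedule does both. It is also background text: it says *should*, and it speaks of a *potential* for margination. The wording is therefore softer than a requirement, and the fall is possible rather than established. That softening stands. The two-occasions reading is less convincing: a transient fall caused by the drug gives little reason to sample only before the first dose, and the sentence itself extends to applicable visits.

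It can also be said that the permission in 7.1.3 was a deliberate amendment. That is so, but Section 1.2 and footnote c were not aligned with it.

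The safeguards are real and limit the point. Section 8.1 presents Table 2 as guidelines, to be applied with clinical judgment and in consultation with the Study Chair. It allows abnormalities of at most 72 hours without important signs or symptoms to be set aside. Table 2 says "Monitor ANC count as clinically indicated", so an early repeat count is possible even though routine draws are 7 days apart in Cycle 1 and about 28 days apart later. In the drug-related row treatment is interrupted, so follow-up counts are taken off drug. These measures are discretionary, however, and a repeat count taken after another dose could show the same fall.

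A reader might go further and infer three things that the documents do not support:

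- **The 6-month response is affected through lower exposure.** The NIH response does not use ANC, no such effect is shown, and Section 1.2 reports that dose reduction did not affect efficacy in Day 28 responders in the acute GVHD study.
- **Change from baseline in ANC is biased downward.** No change-from-baseline analysis is specified (Section 10.4.3), and the size and duration of any fall are unknown.
- **Post-dose samples can never be identified.** The text supports only that the protocol does not require the times.

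**Conclusion.** The point holds in a limited form. Sections 1.2 and 7.1.3 cannot both be followed when a patient doses before the visit, and footnote c of Appendix D conflicts with that option as well. Visit ANC samples may therefore be post-dose, and the protocol does not require the information needed to tell them apart.

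The practical effect is a possible Table 2 action, with its adverse event record, in a patient near the 0.5 x 10^9/L threshold. At an assumed 20% fall this means pre-dose values from 0.50 to just under 0.63. The figure depends wholly on that assumption; for falls of 10% to 40% the upper limit runs from 0.56 to 0.83. It also assumes that the investigator does not apply the exemption or repeat the count. Patients so far below the entry floor are likely to be few, although the documents do not allow a number. The unlabelled mixture in the ANC summaries applies more widely, to any patient who doses before visits, but its size cannot be estimated.

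This is a safety-data and consistency issue. It does not call the primary analysis into question.

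**What to change.** Reconcile Section 1.2, Section 7.1.3 and the order of procedures in Appendix D footnote c, so that one rule on sampling relative to dosing applies at all visits. Which rule it should be is for the sponsor to decide; this review does not choose.

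If dosing before the visit stays permitted:

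- record the time of the last itacitinib dose and the time of the blood draw on the eCRF;
- flag post-dose hematology samples in the database;
- summarise ANC for pre-dose and post-dose samples separately in the safety analysis.

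The cost is a short text change, two eCRF fields, one additional split in a safety table and a small burden on sites. Times for samples already drawn may not be recoverable, so the separate summary may cover only data collected after the change.
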